#### I.4.c. ADVERSE EVENT CODING

The latest version of the AE dictionary, Medical Dictionary for Regulatory Activities (MedDRA), will be used by the CRO staff for the classification and analysis of AEs entered in the study database. For regulatory reporting, SAEs will be processed in the electronic data capture (EDC) system and coded using MedDRA.

#### I.4.d. PREGNANCY

If a subject (or subject's partner) becomes pregnant during the study, it must be reported in within 24 business hours of the time the investigator becomes aware of the event and in accordance with the procedures described on the Pregnancy Report Form. Pregnancy in itself is not regarded as an AE unless there is a suspicion that a study drug may have interfered with the effectiveness of a contraceptive medication. Any pregnancy that occurs from Day 1 to 30 days following the last dose given will be followed for gestational outcome and the outcome would be reported to the Sponsor.

#### I.4.e. CAUSALITY COLLECTION

The investigator will assess the causal relationship (i.e., the relationship to study treatment) between the IP and AEs, and answer "yes" or "no" to the question "Do you consider that there is a reasonable possibility that the event may have been caused by the investigational product?"

Causal relationship in cases where the disease under study has deteriorated due to lack of effect will be classified as no reasonable possibility.

For SAEs, causal relationship will also be assessed. Note that for SAEs that could be associated with any study procedure, the causal relationship is implied as "yes."

A guide to the interpretation of the causality question is found in the MOP.

#### I.4.f. ADVERSE EVENTS BASED ON SIGNS AND SYMPTOMS

All AEs spontaneously reported by the patient in response to the open question from the study personnel: "Have you had any health problems since the previous visit?" or revealed by observation will be collected and recorded in the eCRF. In the collection of AEs, the recording of diagnoses is preferred (when possible) over the recording of a list of signs and symptoms. However, if a diagnosis

is known and there are other signs or symptoms that are not generally part of the diagnosis, the diagnosis and each sign or symptom will be recorded separately.

#### I.4.g. ADVERSE EVENTS BASED ON EXAMINATIONS AND TESTS

The results from protocol-mandated laboratory tests and vital signs will be summarized in the clinical study report (CSR). Deterioration as compared with baseline in protocol-mandated laboratory values and vital signs should therefore only be reported as AEs if they fulfil any of the SAE criteria or are the reason for discontinuation of treatment with the study drug.

If deterioration in a laboratory value/vital sign is associated with clinically significant signs and symptoms, the sign or symptom will be reported as an AE and the associated laboratory result/vital sign will be considered as additional information. Wherever possible, the reporting investigator uses the clinical, rather than the laboratory term (e.g., anemia versus low hemoglobin value). In the absence of clinical signs or symptoms, clinically significant deteriorations in non-mandated parameters should be reported as AE(s).

Any new or aggravated clinically significant abnormal medical finding at a physical examination as compared with the baseline assessment will be reported as an AE.

#### I.4.h. DISEASE PROGRESSION OR WORSENING DEPRESSION

Disease progression can be considered as a worsening of a patient's condition attributable to the disease for which the study drug is being studied. It may be an increase in the severity of the disease under study and/or increases in the symptoms of the disease. The development of worsening depression should be considered as disease progression and not an AE. Events, which are unequivocally due to disease progression, should not be reported as an AE during the study. However, if worsening of depression occurs during ketamine treatment, in the opinion of the investigator, is to be reported as an adverse event.

#### I.4.i. SERIOUS ADVERSE EVENTS (SAEs)

The EDC platform will provide a mechanism for sites to report SAEs, and for the Site Investigators and MGH CTNI Medical Monitor to sign off on the SAE reports. Reportable (related and/or unexpected) SAEs will be sent to the Sponsor or their designee within regulatory timelines.

##### I.4.i.1. DEFINITION OF SAEs

The following criteria define a SAE:

- Death
- Life-threatening event
- Hospitalization or prolongation of hospitalization
- Persistent or significant disability/incapacity
- Congenital anomaly/birth defect

- Medically important event, as defined in this protocol\*

\*Medical and scientific judgment will be exercised in deciding whether expedited reporting is also appropriate in other situations, such as important medical events that may not be immediately life threatening or result in death or hospitalization but may jeopardize the subject or may require intervention to prevent one of the other outcomes listed in the definition above. These will usually be considered serious.

#### I.4.i.2. REPORTING OF SAEs

When a SAE is discovered at the site, it will be reported immediately (within 24 business hours), as described below. Reportable serious adverse events will be reported according to the central IRB reporting policy and FDA regulations. Reportable events may include (but will not be limited to): (a) changes in the health status of the patient, (b) unexplained or severe psychiatric complications, and (c) clinically significant development or worsening of suicidal ideation or behavior. The Site Investigator will determine whether the event is study-related. All reportable serious adverse events will be reported by CTNI within 48 business hours to the CTNI medical monitor and the study site PIs.

### I.5. PROTOCOL WAIVERS AND VIOLATIONS

#### I.5.a. PROTOCOL WAIVERS

Protocol waivers will not be allowed for this study.

#### I.5.b. PROTOCOL VIOLATIONS

##### I.5.b.1. PROCEDURE FOR NON-COMPLIANT PATIENTS

Patients will be scheduled for the period of study participation when they are available to come in for study visits. Patients who miss one visit will be allowed to make up that visit within a window that depends on the visit. Every effort will be made by the site to adhere to the study visit schedule, in order for assessments to be able to be performed at the stipulated time points. Patients who miss more than one visit will be discontinued from the study. However, patients who either complete the study or discontinue prematurely will be eligible for three months of free care at the clinic where they were enrolled. Patients who withdraw consent will no longer have data collected for the study. Every effort will be made to maintain contact with patients who are discontinued, but who do not withdraw consent, according to the study schedule (Table 3) for 30 days post-treatment in order to collect safety data.

I.5.b.2. PROTOCOL VIOLATION DEFINITIONS

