#### I.1.o. EARLY TERMINATION VISIT

If a patient is terminated from the study before completion, but after at least one dose of ketamine and/or study drug, the procedures listed in Table 3 for Visit 11 (Day 28) should be completed.

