### I.3. DISCONTINUED SUBJECTS

Sites will follow the procedures in Section I.1.o. for discontinued patients.

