#### J.6.a. PROCEDURES FOR DISCONTINUATION FROM STUDY TREATMENT

#### J.6.a.1. MEDICAL REASONS FOR DISCONTINUATION

In the event that the patient's blood pressure rises to an unacceptable level during treatment, in the opinion of the attending physician, the physician will discontinue treatment and initiate appropriate measures according to usual medical practice.

A patient who decides to discontinue participation in the study will always be asked about the reason(s) and the presence of any AEs. If possible, they will be seen and assessed by an investigator. AEs will be followed up until resolution (see Section I.4.b).

If a patient discontinues from the study before randomization, then no further follow-up will be expected. However, if the patient discontinues after randomization, but before receiving any study treatment, the patient will be asked to return for a final study visit, during which the procedures outlined in the Early Termination Visit procedures will be completed, including AEs and concomitant medication assessments.

If a patient discontinues from the study before completion and has received a dose of study drug, the patient will be asked to return for a final study visit, at which the procedures outlined in the Early Termination Visit will be completed. Every effort should be made to follow up with patients who discontinue from the study prior to Visit 11 (Day 28). If patients refuse to return to the clinic for the study-related assessments, a modified follow-up through, for example, regular telephone contact or a contact at study closure should be arranged, if agreed to by the patient and in compliance with local data privacy laws/practices. If the patient refuses follow-up, the reason for the refusal and last contact date should be documented in the eCRF and source documents.

Patients who discontinue from the study will not be replaced.

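### The missed-visit rule removes patients who still consent, and nothing requires their Day 14 or Day 28 SDQ afterwards

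*Combined protocol and SAP*

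**What the plan says.** All references are to the combined protocol and SAP.

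- **Removal.** Section I.5.b.1: "Patients who miss more than one visit will be discontinued from the study". This is removal from the study, not only from treatment. Section I.5.a allows no waivers.
- **Make-up visits.** Section I.5.b.1 also says: "Patients who miss one visit will be allowed to make up that visit within a window that depends on the visit". Table 3 gives windows of ±2 to ±4 days from Visit 4 on and none for Visits 2 and 3. The text does not say whether a made-up visit still counts as missed.
- **Contact afterwards.** For discontinued patients who have not withdrawn consent, Section I.5.b.1 plans contact on the Table 3 schedule "for 30 days post-treatment in order to collect safety data".
- **Exit visit.** Section I.3: "Sites will follow the procedures in Section I.1.o. for discontinued patients". Section I.1.o then requires that "the procedures listed in Table 3 for Visit 11 (Day 28) should be completed". Those procedures include the SDQ.
- **Wider follow-up.** Section J.6.a.1 asks sites to try to follow anyone who leaves ahead of Visit 11 (Day 28). It continues: "If patients refuse to return to the clinic for the study-related assessments, a modified follow-up through, for example, regular telephone contact". Day 28 appears there as the cut-off for early discontinuation, not as a day on which the SDQ must be collected. The section also states: "Patients who discontinue from the study will not be replaced".
- **Analysis.** Section N fits a linear mixed model by REML to all available data, with the Day 14 SDQ difference as the primary contrast. It states no sensitivity analysis for missing data. Day 28 SDQ is a secondary aim (Section F.2).

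**The concern.** The SDQ is listed as an efficacy measure in Section I.2.d.2, so a site reading Section I.5.b.1 would reasonably conclude that it is not collected once a patient has been removed. A site reading Section J.6.a.1 might conclude otherwise, but would not find the instrument or the collection days named. Under the narrower reading, someone who misses two early visits and is willing to attend on Day 14 has no Day 14 SDQ, because the rule rather than the patient ended assessment.

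The mixed model keeps that patient's earlier scores, which helps. It then relies on the unseen values being missing at random given what was observed. If visits are missed because of poor tolerability or lack of benefit beyond what earlier scores show, that assumption may fail. The documents do not show that this happens. The point is that the plan can create missing values it could largely avoid creating.

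**Working it through.** **The plan's own figure.** Section N gives 26 per arm for 80% power at a standardised difference of 0.8, two-sided 0.05. A two-sample noncentral t calculation gives a smallest n of 26 per arm (power 80.7%). The figure reproduces and contains no allowance for lost values. It is not in dispute, and no power loss is derived from it below.

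**Inputs from the documents.** Five post-baseline visits precede Day 14 (Visits 2–6). Nine precede Day 28 (Visits 2–10). Removal follows the second counted miss.

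**Assumptions.** The documents give no missed-visit rate, so take p = 5%, 10% or 15% per visit, independent across visits. Count only patients who would have attended the target visit, since the rule costs nothing in those who would have missed it anyway.

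**Formula.** Share of values lost to the rule = P(Bin(k, p) ≥ m) × (1 − p), with k = 5 for Day 14 and k = 9 for Day 28. Set m = 2 if no miss is made up, and m = 3 if one miss is made up and not counted.

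**Worked at p = 10%.**

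- Day 14, m = 2: 1 − 0.9^5 − 5(0.1)(0.9^4) = 1 − 0.59049 − 0.32805 = 0.08146; × 0.9 = 0.0733.
- Day 14, m = 3: 0.08146 − 10(0.01)(0.729) = 0.00856; × 0.9 = 0.0077.
- Day 28, m = 2: 1 − 0.38742 − 0.38742 = 0.22516; × 0.9 = 0.2026.
- Day 28, m = 3: 0.22516 − 36(0.01)(0.47830) = 0.05297; × 0.9 = 0.0477.

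| Reading | Day 14, p = 5 / 10 / 15% | Day 28, p = 5 / 10 / 15% |
|---|---|---|
| One miss made up and not counted (m = 3) | 0.1 / 0.8 / 2.3% | 0.8 / 4.8 / 12.0% |
| No miss made up (m = 2) | 2.1 / 7.3 / 14.0% | 6.8 / 20.3 / 34.0% |

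At p = 15%, out of 52 patients, the first row is 52 × 0.0226 = 1.2 at Day 14 and 52 × 0.1197 = 6.2 at Day 28. The second row is 52 × 0.1401 = 7.3 and 52 × 0.3404 = 17.7.

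**Crediting the exit SDQ.** Both rows are before any such credit. Visit 6 closes on Day 13 and the Day 14 window is Days 12–16, so a prompt exit visit after removal at Visit 6 could fall in that window. Visits 9 and 10 close on Days 24 and 27 and the Day 28 window is Days 24–32, so the same holds there. Crediting these reduces k to 4 and 7:

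- No miss made up: 1.3 / 4.7 / 9.3% at Day 14 and 4.2 / 13.5 / 24.1% at Day 28.
- One miss made up and not counted: 0.05 / 0.3 / 1.0% and 0.4 / 2.3 / 6.3%.

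This credit is generous, because no rule in the plan assigns an exit SDQ to a visit.

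**The case against.** **The follow-up wording is broader than one section.** A reader might infer that the whole protocol limits contact after removal to safety. It does not. Section J.6 lists protocol violation among the reasons for discontinuation, so Section J.6.a.1 can cover these patients, and its follow-up is not restricted to safety. Section I.5.b.1 itself refers to Table 3, which lists the SDQ at every visit. This stands: the sections can be read together. What remains is that neither says the SDQ continues at Days 14 and 28, and the one purpose given in Section I.5.b.1 points the other way.

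**An SDQ is collected at exit.** A reader might also infer that removal ends efficacy data at once. Sections I.3 and I.1.o rule that out. But a score at about the time of removal stands in for Day 14 or Day 28 only if it happens to fall in that window.

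**The large figures are upper cases.** The protocol allows a make-up visit, schedules participation for when patients are available, and pays for attendance. The 14.0% and 34.0% figures need the highest assumed rate, no make-up at all and no exit credit. They are not forecasts. Independence is also an assumption. If misses cluster in the same patients, more may reach the threshold, but those patients are less likely to have attended the target visit. The documents cannot settle the net direction.

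**Power.** It is tempting to turn these losses into a drop from 80.7%. That would be wrong: the same miss model also removes Day 14 values with no rule in place, so 80.7% is not the right base, and the mixed model recovers part of the loss from earlier visits. No power figure is claimed.

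**Estimand.** Scores taken after removal may be off study drug, and Section I.5.b.1 offers three months of free care, so they may also reflect other treatment. This stands. It is a reason to decide their role in advance, not to leave collection unclear.

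**Conclusion.** The concern holds in limited form. The plan actively removes consenting patients for missed visits and does not require the primary or secondary SDQ time point afterwards. With one miss made up and not counted, the Day 14 loss is 0.1% to 2.3%, so the effect on the primary analysis is probably small. Day 28 is more exposed, at 0.8% to 12.0%, because more visits have accrued. Without make-ups the upper cases are higher at both days, and the gap between the two readings shows why it matters whether a made-up visit counts. All sizes rest on assumed, independent miss rates of 5% to 15%.

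A reader might go further and infer biased results or a failed primary analysis. The documents do not support that: they give no miss rate and no evidence that missed visits relate to outcome. This is a cheap improvement that should be made.

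**What to change.** 1. Reconcile Section I.5.b.1 with Section J.6.a.1. Separate leaving treatment from leaving assessment: unless consent is withdrawn, collect the self-rated SDQ at least at Days 14 and 28, remotely if needed, during the contacts already planned. Contact for 30 days after treatment passes Day 28 even for a patient whose only dose was on Day 0 (0 + 30 = 30).
2. State whether a made-up visit counts as missed.
3. Analyse the early-termination SDQ at its actual study day.
4. Fix in advance whether SDQ scores taken after study treatment stops enter the primary model or a sensitivity analysis.

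Rules for stopping treatment are unchanged.

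**Cost.** Protocol wording and a few questionnaires. The downside is that some scores will be taken off study drug, possibly under other care, and by a remote mode that the protocol does not describe for the SDQ. Recovery will be partial, since some patients who miss visits will not respond.

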**TABLE 5 - LIST OF EXAMPLES OF PROTOCOL VIOLATIONS**

	Major Protocol Violation	Minor Protocol Violation
The list of examples is intended as a guide and is not all-inclusive.		
Definition	A violation that may :  Impact subject safety,  Affect the integrity of study data, and/ or  Affect the subject’s willingness to participate in the study.	A violation that does not :  Impact subject safety,  Compromise the integrity of study data, and/ or  Affect the subject’s willingness to participate in the study.
Examples  (not all-inclusive)	
Failure to obtain informed consent
 
Informed consent obtained by an unauthorized individual
 
Enrollment of a subject who did not meet eligibility criteria for whom a protocol exception was not obtained
 
Performing a study procedure that is not approved by the IRB and/or is not in the protocol
 
Failure to perform a required lab test that, in the opinion of the Site Investigator, may affect subject safety or data integrity
 
Failure to perform or follow a study procedure that, in the opinion of the Site Investigator, may affect subject safety or data integrity
 
Failure to follow safety (AE) management plan
 
Failure to report a SAE to the IRB and/or Coordination Center
	
Implementation of unapproved recruitment procedures
 
Only a photocopy of the signed/ dated consent form is available (the original is missing)
 
Pages are missing from the signed/ dated informed consent form
 
Use of invalid consent form (i.e., without IRB approval or outdated/expired form)
 
Failure to perform or follow an approved study procedure that, in the opinion of the Site Investigator, does not affect subject safety or data integrity
 
Study procedure conducted out of sequence
 
Failure to perform a required lab test
 
Missing lab results
 
Study Visit out of approved window
 
Over-enrollment

		Enrollment of subjects after IRB approval of the study has expired  Failure to submit a continuing review application to the IRB before study expiration
Reporting Requirements	Record the date discovered, date occurred, description of event in the Protocol Deviation Log.  Notify the Coordinating Center within 24 business hours.	Record the date discovered, date occurred, description of event in the Protocol Deviation Log.  Notify the Coordinating Center

I.5.b.3. PROTOCOL VIOLATION REPORTING

Protocol violations will be reported as described in the MOP.

J. TREATMENT

J.1. DOSING SCHEDULE

Ketamine 40 mg will be administered intranasally six times during the study. Ketamine will be administered at the respective visits, by study staff, onsite. Brexpiprazole or matching placebo will be administered orally daily for 28 days according to the fixed-flexible dose escalation schedule.

J.2. STUDY PRODUCT SUPPLIES AND ADMINISTRATION

Intranasal ketamine will be prepared as described in the Manual of Procedures. The intranasal ketamine will be supplied in a metered MAD Nasal™ Intranasal Mucosal Atomization Device. Each Intranasal Mucosal Atomization Device will contain 1mL of 40mg/mL Ketamine and be used for one administration. A total of two sprays, with one spray (a volume of 0.5 mL) given in each nostril, will be administered. A total of six atomization devices will be prepared for each patient.

Brexpiprazole and matching placebo, in .5 mg and 1 mg tablets, will be supplied to each site by Otsuka Pharmaceuticals. The site pharmacist will package the brexpiprazole and placebo tablets in bottles, and supply 4 bottles for each patient, according to the randomization scheme. Each bottle will contain 10, 20 or 30 pills, according to the dosage requirements listed below, of either brexpiprazole or placebo, and be labeled with the randomization number for that patient.

**TABLE 6 BREXPIPIRAZOLE DOSING**

Visit/Day	Visit 1/Day 0	Visit 5/Day 8	Visit 7/Day 14	Visit 9/Day 21
Dose/day	.5 mg	1mg	2 mg	3 mg
Number of Pills per Dose	1	1	2	3
Number of Pills per Bottle	10	10	20	30

### J.3. PACKAGING AND LABELING

#### J.3.a. CONCOMITANT OPEN-LABEL ADT

Open-label ADT will be provided to allow for continuing the same dose of ADT throughout the study. The amount of open-label study medication (ADT) dispensed to a patient at any given visit is contingent upon the prescribed daily dose of ADT. ADT will be provided through prescriptions, and patients will be reimbursed for any out of pocket expenses they incur for filling the prescription.

#### J.3.b. BLINDED BREXPIRAZOLE/PLACEBO THERAPY

Blinded study drug will be provided to each subject at Visits 1, 5, 7 and 9, and a pill count will be performed by study site personnel at each study visit. Patients will be instructed to bring their pill bottles to every visit.

### J.4. DOSE MODIFICATION FOR TOXICITY

Dose modifications will be allowed, if patient cannot tolerate the dose increases. If a dose modification is necessary, patients should return to the previous tolerable dose.

### J.5. CONCOMITANT THERAPY

All concomitant medications taken during the study will be recorded in the Concomitant Medication Log for each patient, along with dosage information and start and stop dates. Allowed concomitant medications include any prescription or over-the-counter medication not specifically excluded by the protocol (see Appendix 1), as well as stable, ongoing antidepressant therapy and stable allowed hypnotic therapy. Patients requiring excluded drugs will be discontinued from the study.

### J.6. DISCONTINUATION FROM STUDY TREATMENT

Every effort will be made to keep the patient in the study for the full study period consisting of one day of acute treatment plus 6 follow-up assessments. Acceptable reasons for early discontinuation include the following: 1) request of patient, 2) decision of physician, 3) serious adverse event, and 4) protocol violation.

